(1) Age > 3 years but below 18 years (2) Elective surgery (3) American Society of Anesthesiologists physical status 1-3 (Free from major concurrent disorders) (4) Free from nausea and / or vomiting in the previous 24 hours (5) Cognitive, visual, hearing and communicative ability to use the VAS as shown by the ability to complete a seriation task in which children pick the biggest of 6 cut out shapes, then the smallest, and the biggest remaining until no shapes remain (Beyer et al: J Pediatr Nurs 1992; 7: 335-46)

Exclusion Criteria:

(1) Developmental delay (2) Blindness (3) Impaired cognitive or communicative abilities including inability to rate the intensity of symptoms and failure to complete the seriation task (4) Surgical procedures which may result in diminished hearing or vision in the immediate postoperative period (5) Nausea and /or vomiting within 24 hours prior to the procedure (6) Inability to understand English, (7) Patient or parental refusal to participate (8) Pregnant females

F2. Procedure

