We will first determine if the child will qualify for the study by showing 6 cut out shapes of different sizes and asking the child to first choose the largest size, then the smallest, then the largest remaining size until no more shapes are left. If the child qualifies for the study and if they agree to participate, we will obtain baseline values as described below. Baseline Values: Baseline assessments of nausea before the procedure would be obtained from the awake child using both the visual analogue scale and the BARF scale. The order in which the first scale is presented to the patient for assessment will be randomized to reduce the potential for an order effect. The script for the scales would be standardized in keeping previous studies. For the nausea scales, the script would be: "Have you thrown up or felt like you were going to throw up before? How did your tummy feel then? We call that feeling of being sick to the stomach as nausea. VAS Scale: On this line the far left indicates "No nausea" and the far right? Worst nausea ever." Can you show me on this line how much nausea you have right now? Faces Scale: "These faces show children who feel no nausea at all, who feel a little bit nauseous, who feel even more nauseous, and these are children who have a lot of nausea." (Point to the each face at the appropriate time). Which face is more like you right now?" The evaluator will assess if the child has understood the instructions and has the ability to provide a reliable response.

Perioperative Care

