The study has a number of aims and the power analysis is provided separately for each aim: (1) In order to examine the age related ability to use the BARF scale we will recruit 28 subjects each in the ages of 3, 4, 5, 6, 7, 8, 9, 10, 11, 12 and >12 years years (28 X 11 = 308). Power analysis was based on an alpha of 0.05, power of 80% and a large effect size (Cohen's d = 0.80) as it was assumed a large difference would be needed for the results to have clinical utility (Pain 2011; 152: 1327-33). This suggested a group size of 24 would be needed. Allowing for a drop out rate of 20% we plan to recruit 28 in each of the 11 groups. (2) Power analysis for minimum clinically relevant difference in BARF scores: A one face difference in the BARF scale is the minimum difference that can be detected. A previous study showed that the mean BARF scores in the postoperative period in children was 1.6 +/- 2.4 (Pediatrics. 2011 Jun;127(6):e1542-9) . In order to detect a 1 face difference with 80% power at the 0.05 level of significance we will need 93 subjects who had a change in their nausea scores. Assuming an incidence of postoperative nausea and vomiting (PONV) of 33% (which is similar to previous data in children), a group size of 93 X3= 279 will be required to obtain 93 subjects with a change in nausea scores. We plan to recruit 387 subjects to allow for a 35% dropout rate.

This sample size will have a >80% power for the other aims of the study (The BARF and VAS scores associated with a patient's perception of the need for treatment and the test - retest reliability of the VAS and BARF scores when nausea is rated as unchanged.)

G2. Data Analysis

Provide a description of your plan for data analysis. State the types of comparisons you plan (e.g. comparison of means, comparison of proportions, regressions, analysis of variance). Which is the PRIMARY comparison/analysis? How will the analyses proposed relate to the primary purposes of your study?

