Statistical Analysis: (1) The mean and SD of all scores will be calculated along with their distribution. The incidence of postoperative nausea and postoperative vomiting in the PACU and after discharge (post-discharge nausea) will be calculated. The incidence of severe nausea (score>6 on the BARF scale) and severe vomiting (3 or more episodes over 24 hours) will also be determined. (2) We will record the age of a child and their ability to rate their nausea on the BARF and VAS scales to determine the minimum age where a patient can reliably use the scale. (3) Changes in BARF and VAS nausea scores will be calculated for subjects who report their nausea as a little worse than before or a little better than before, to determine the minimum change in scores of clinical relevance. (4) The BARF score and its relationship to the request for rescue antiemetics will be examined by a Spearman's rank correlation. (5) The relationship between the first and subsequent BARF and VAS nausea scores in patients who state their nausea is 'the same as before?' will be examined by a Spearman's rank correlation and a Cronbach's alpha calculation. This will provide the test ? retest reliability.

Section H: Potential Risks/Discomforts

Describe and assess any potential risks/discomforts; (physical, psychological, social, legal, or other) and assess the likelihood and seriousness of such risks:

The risks are limited to possible loss of confidentiality as there are no changes in surgical or anesthetic management of the child other than obtaining data on estimating the degree of nausea. Loss of confidentiality is unlikely in view of standard steps taken to avoid this.

Section I: Potential Benefits

Describe potential benefit(s) to be gained by the individual subject as a result of participating in the planned work.

Subjects will not have any direct immediate benefits from participating in these studies.

Describe potential benefit(s) to society of the planned work.

Determining the clinical utility of a faces pain scale will facilitate treatment and research into this clinically important realm of suffering for children of all ages. Future patients may benefit from having such a tool as it will permit clinicians to measure the symptom severity and then treat such patients

Do anticipated benefits outweigh potential risks? Discuss the risk-to-benefit ratio.

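### Inability to rate symptoms is both an exclusion (F1) and the outcome of analysis (2) (G2); if children found unable at baseline are excluded, the minimum age comes out too low

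*Combined protocol and SAP*

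**What the plan says.** F1, exclusion (3), reads "Impaired cognitive or communicative abilities including inability to rate the intensity of symptoms and failure to complete the seriation task". Inability to rate is named in addition to failing the seriation task, so the criterion reaches beyond the seriation screen. Refusal is separate, as exclusion (7): "Patient or parental refusal to participate".

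F2 sets the order of events. Screening comes first: "We will first determine if the child will qualify for the study by showing 6 cut out shapes of different sizes". Then: "If the child qualifies for the study and if they agree to participate, we will obtain baseline values as described below". During these baseline ratings, "The evaluator will assess if the child has understood the instructions and has the ability to provide a reliable response". This is the only place where the documents describe a check of ability to rate. They do not say what counts as able, or what happens to a child judged unable.

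G2, analysis (2), records each child's age and ability to rate on both scales, "to determine the minimum age where a patient can reliably use the scale". It gives no denominator, no threshold for reliable use and no rule for a failed or missing rating.

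G1 sizes the age aim at 24 per group and adds: "Allowing for a drop out rate of 20% we plan to recruit 28 in each of the 11 groups". Dropout is not defined.

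**The concern.** A child who has passed seriation, enrolled and then cannot use a scale is the event that analysis (2) must count. Under exclusion (3), read literally, the same child should not be in the study. The check that would reveal the inability comes after qualification and agreement, so the two provisions meet at that point, and site staff have no instruction on which prevails.

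If the exclusion prevails, the children who define the lower age limit disappear from the calculation, probably most often in the youngest groups. Estimated ability rises, the age gradient flattens and the minimum age falls. The lowest age of reliable use is one of the open questions that the background gives as a reason for the study, and age differences in the two scales are objective (2) in Section D. The criterion is also not specific to a scale. A child who fails on the VAS but manages the BARF scale is informative for comparing them, and could be lost to both.

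**Working it through.** **The plan's own figure.** For d = 0.80, two-sided alpha 0.05 (sidedness is assumed; the plan does not state it) and 80% power, the size per group is 25 by the normal approximation or 26 by the t-test, against the stated 24. The total 28 × 11 = 308 checks. Going from 28 to 24 allows for 4/28 = 14.3% loss; a 20% loss would leave 28 × 0.80 = 22.4. These small differences do not decide the point, which concerns who is in the denominator and not how many are recruited.

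**Effect of removing failures.** Let p be the true share of enrolled children in an age group who can rate, and f the share of failures removed. Then

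observed ability = p / [p + (1 − p)(1 − f)].

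The documents give neither p nor f, so every value below is an assumption.

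| True p | f = 0 (all counted) | f = 0.5 | f = 1 (all removed) |
|---|---|---|---|
| 50% | 50% | 67% | 100% |
| 60% | 60% | 75% | 100% |
| 70% | 70% | 82% | 100% |
| 80% | 80% | 89% | 100% |
| 90% | 90% | 95% | 100% |

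In whole children, with 28 in an age group of whom 6 cannot rate:

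- all counted: 22/28 = 79%
- three of the six removed: 22/25 = 88%
- all removed: 22/22 = 100%

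**Effect on the minimum age.** This needs an age curve and a cut-off, and the plan gives neither. Assume a logistic curve, ability = 1/(1 + exp[−slope × (age − midpoint)]), and take the minimum age as the first whole year with observed ability of at least 80%.

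| Midpoint, slope per year | All counted | Half removed | All removed |
|---|---|---|---|
| 3.5 years, 1.0 | 5 | 5 | 3 |
| 3.5 years, 1.5 | 5 | 4 | 3 |
| 4.0 years, 1.0 | 6 | 5 | 3 |

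Removing half the failures lowers the minimum age by a year on two of the three curves and leaves it unchanged on the other. Removing all of them gives 100% at every age, so the answer is always the youngest group recruited and the data no longer identify a minimum age.

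**The case against.** The strongest reply is that the plan does not prescribe removal. Analysis (2) says that ability to rate will be recorded by age, which makes sense only if inability is recorded too, and the evaluator's baseline judgement may be where that happens. Exclusion (3) is an entry criterion, and F2 places entry before the ratings. This stands as far as it goes: a reading that keeps the failures is open, and under it there is no bias. It does not remove the conflict. Exclusion (3) names inability to rate separately from seriation failure, and the only described check of that ability comes after enrolment.

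Some stronger inferences should be resisted.

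- *That the dropout allowance is largely made up of children who cannot rate.* G1 neither defines dropout nor links it to non-rating, and withdrawal, cancelled surgery or ratings missed by staff are other possible causes. The 35% allowance belongs to the minimum-difference aim and the total of 387, not to the age groups of 28, so it cannot be applied to them.
- *That a child who will not rate meets exclusion (3).* Unwillingness is not inability. Exclusion (7) covers refusal to take part, and declining a single rating is not addressed.
- *That every missing PACU rating should count as a failure.* That would treat sedation, distress or unwillingness as age-related incapacity and could push the minimum age too high.

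**Conclusion.** The point holds as a conflict between a stated exclusion and a stated outcome, with no rule to settle it. If exclusion (3) is applied at the baseline check, the minimum age is biased low. A reader might infer that the plan will certainly lose its failures, or that any age group would cross any reasonable cut-off. The documents support neither: removal is one of two open readings, the plan states no cut-off, and one of the assumed curves shows no shift when half the failures are removed.

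The documents do not fix the size. It is nil if failures are kept. If 6 of 28 could not rate and all were removed, it would be 21 percentage points (100% against 79%). The direction rests on one assumption only, that some enrolled children who have passed seriation still cannot rate. The effect on the minimum age also rests on the assumed curves and the 80% cut-off. The matter should be settled because it bears on a stated objective and costs little to resolve.

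**What to change.** - **F1.** Limit exclusion (3) to cognitive or communicative impairment known before entry, plus seriation failure. Delete inability to rate as a ground for removal after enrolment.
- **G2, analysis (2).** State that the denominator is all enrolled children in the age group who were asked at baseline. Score a child judged unable to understand or respond on a scale as unable for that scale. State the criterion the evaluator uses for able.
- **Missing ratings.** Record the reason at each time point: unable, drowsy or distressed, declined, missed by staff, withdrawn or cancelled. Keep PACU non-rating due to sedation, distress or refusal separate from unable, with a sensitivity analysis that counts it as unable.
- **G2, analysis (1).** Report the number not rated, by age, beside the PACU nausea incidence, so that readers can see which children the incidence describes.

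The cost is a few sentences and one reason-not-rated field. Neither the sample size nor patient care changes. Ability figures in the youngest groups may look less favourable.

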Pediatric research in the management of nausea has been limited by the absence of a reliable method to quantify the intensity of this subjective symptom. In adults, the visual analog scale (VAS) is an accurate tool, but this has not been shown to be reliable in young children. By default the most common objective outcome measure used in pediatric studies has been the incidence and number of emetic episodes. This measure, however, correlates poorly with the somatic subjective symptom of nausea.

Apfel et al have shown that 30-40% of adult patients undergoing surgery have post discharge nausea and / or vomiting while 12% have vomiting. These data on nausea in adults were based on a visual analog scale for nausea. There are no data on the incidence of postoperative nausea in children since the severity of symptoms are difficult to measure as younger children are known to be unable to use the VAS reliably.

Recently a pictorial scale for measuring nausea, the Baxter Animated Retching Faces (BARF) scale, has been developed and shown to have construct, content and convergent validity as an instrument to measure nausea in children. The clinical usefulness of this scale in determining the incidence of postoperative and post-discharge nausea in children has yet to be determined including the lowest age where it can be used reliably, the score associated with a patient's perception of a need for treatment, the minimum change in the scores of clinical relevance and the test-retest reliability when nausea is rated as not having changed.

Section D: Purpose and Objectives

This study in the pediatric patient population is designed to determine: (1) The incidence of postoperative

nausea as compared to postoperative vomiting in the Post Anesthetic Care Unit (PACU) and on discharge (Post Discharge nausea and Vomiting). (2) The age related differences in the reliability and usefulness of the BARF and VAS scales for measuring nausea. (3) The minimal clinically relevant differences in nausea on the BARF and VAS scales. (4) The BARF and VAS scores associated with a patient's perception of the need for treatment. (5) The test - retest reliability of the VAS and BARF scores when nausea is rated as unchanged.

Section E: Protocol Risks/Subjects

E1. Risk Category

Category 1: Research not involving greater than minimum risk.

E2. Subjects

Gender:

Both

Age:

Adolescent (13-17 yrs), Child (3-12 yrs)

Ethnicity:

All Ethnicities

Primary Language:

English

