After providing baseline values in the preoperative holding area, the patient's anxiety would be assessed using the validated modified Yale Preoperative Anxiety scale (mYPAS) (12), while the child is in the holding area, at the time of separation and when the face mask is applied during induction of anesthesia. The child would receive general anesthesia. The choice of drugs, techniques and perioperative management, including the need (if any) for preoperative medication, will be determined by the Attending Anesthesiologist according to the clinical needs and will not be changed for the purposes of the study. The patient will be monitored in keeping with the standards and policies of the department of Anesthesiology, Texas Children's Hospital. All Perioperative data will be collected via medical record review. In the Post Anesthetic Care Unit (PACU) patients will receive standard care, including analgesic or antiemetic therapy as prescribed by the Attending Anesthesiologist based on his opinion of the clinical needs of the situation. When awake, the patients will be asked to rate their nausea on both scales (VAS and BARF for nausea). The order of presentation of scales will be the same as in the preoperative area. If a child receives analgesic or antiemetic therapy, he/she will be asked to rate the pain and nausea immediately before receiving the drug and 30-60 minutes after receiving treatment. In summary, patients will rate their nausea using the VAS and BARF scales for nausea at these

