time points: (1) before induction of anesthesia, (2) when awake in the PACU, (3) just before, and (4) 30-60 mins after receiving analgesic or antiemetic therapy and (5) just before discharge home. The order of presentation of scales will be randomized but the same for all time points for an individual subject. After the first set of assessments are done in the PACU, patients will also be asked to rate their nausea on a 5 point Likert scale as : (1) Much worse than before, (2) A little worse than before, (3) The same as before (4) A little better than before and (5) Much better than before. They will also be asked if they want any treatment of their nausea. Another set of assessments will be just prior to discharge. All other aspects of patient management will be the standard care given to such children at the Texas Children's Hospital. Patients will be discharged from the PACU when they have achieved the standard criteria set for discharge at the TCH. At the time of discharge we will give the parents a diary to record the the MAXIMUM nausea on the VAS and BARF scales and mail it back in a stamped envelope. We will phone them about 24 hours after surgery and ask if the child had any nausea, vomiting and what medications were used after going home. We will ask the parent to rate their satisfaction with the control of nausea and with the entire perioperative experience on a 0-10 scale. We will remind them to mail the nausea assessments back and to state which face represented the maximum nausea after discharge.

Section G: Sample Size/Data Analysis

G1. Sample Size

How many subjects (or specimens, or charts) will be used in this study?

Local: 387 Worldwide: 387

Please indicate why you chose the sample size proposed:

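### Objective 1 sets PACU nausea, which the study elicits, against PACU vomiting, which no study procedure asks about or counts; the contrast mixes a real difference with a difference in method.

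*Combined protocol and SAP*

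**What the plan says.** All references are to the combined protocol and SAP.

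- **Objective (Section D, item 1).** The study is to determine the incidence of postoperative "nausea as compared to postoperative vomiting in the Post Anesthetic Care Unit (PACU) and on discharge". G2 item (1) plans to calculate both incidences in the PACU and after discharge, and adds severe vomiting, defined as three or more episodes over 24 hours.
- **Nausea in the PACU (F2).** It is elicited from the child: "When awake, the patients will be asked to rate their nausea on both scales (VAS and BARF for nausea". Postoperative ratings are scheduled on waking in the PACU, on either side of any analgesic or antiemetic dose (the second one 30-60 minutes later), and shortly before the child leaves. The VAS script asks about the present moment: "Can you show me on this line how much nausea you have right now". The child also gives a five-point rating of change in nausea and is asked about wanting treatment for it.
- **Vomiting in the PACU (F2).** No question, observation or count is described. The general statement on sources, under Perioperative Care, is "All Perioperative data will be collected via medical record review".
- **After discharge (F2).** A telephone call about 24 hours after surgery will "ask if the child had any nausea, vomiting and what medications were used after going home". The take-home diary records maximum nausea on both scales and has no entry for vomiting.

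**The concern.** When two incidences are set side by side, the reader takes the gap between them as a fact about the children. That holds only if both are ascertained in comparable ways. Here one is prompted, prospective self-report at set moments. The other, as far as the document shows, is whatever routine care happened to chart. A gap between them could be clinical, could come from the method, or could be both, and the planned data would not let anyone separate the parts.

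This matters because the background section argues that emetic counts are a poor guide to nausea, and Objective 1 is where the study reports the two together. It also affects comparison over time: vomiting after discharge is asked about directly by phone, so PACU and post-discharge vomiting would differ in method too.

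A second output is affected. Severe vomiting is defined by a count over 24 hours, and no described procedure produces that count.

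**Working it through.** The document gives no expected contrast, power or sample size for Objective 1, so there is no figure of the plan's own to reproduce. The check sets the procedures side by side and then works out which way each kind of missed event moves the result.

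**1. Ascertainment as described**

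| | Nausea | Vomiting |
|---|---|---|
| PACU, every child | Asked on waking and just before discharge | No study procedure |
| PACU, if an analgesic or antiemetic is given | Also asked just before and 30-60 minutes after | No study procedure |
| PACU, time covered by each rating | The present moment | Not stated |
| PACU, stated source | Child's VAS and BARF rating | Medical record review, by inference |
| After discharge | Phone question, plus diary of the maximum | Phone question only |

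An untreated child thus has two momentary nausea ratings for the whole PACU stay.

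**2. Direction of the error**

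Let N and V be the true PACU incidences of nausea and vomiting, and let s_N and s_V be the fractions of affected children captured. Assume no false reports.

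- Observed difference = s_N × N − s_V × V
- Error in the difference = (1 − s_V) × V − (1 − s_N) × N
- Observed ratio ÷ true ratio = s_N ÷ s_V

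The documents give neither s_N nor s_V. Three assumed pairs show the range of behaviour:

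| s_N | s_V | Multiplier on the ratio | Error in the difference |
|---|---|---|---|
| 1.0 | 0.8 | 1 ÷ 0.8 = 1.25 | +0.2V: widened |
| 0.8 | 0.8 | 0.8 ÷ 0.8 = 1.00 | 0.2(V − N): narrowed if N > V |
| 0.8 | 0.9 | 0.8 ÷ 0.9 = 0.89 | 0.1V − 0.2N: narrowed if N > V/2 |

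The contrast can be exaggerated, unchanged on the ratio scale, or understated, depending on two quantities that the plan neither measures nor states. The multipliers illustrate direction only; they do not estimate what would happen in this study.

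**3. The severe-vomiting outcome**

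The 24-hour count is the PACU episodes plus the episodes after leaving. No PACU count is described. The call is described as asking whether there was any vomiting after going home, and a yes to that is compatible with one episode or with several. The threshold of three therefore cannot be applied from the described procedures alone, whatever the quality of the chart for the PACU period.

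**The case against.** **The chart is not named as the source of PACU vomiting.** This stands: it is an inference. The record-review sentence follows the text on anesthetic drugs and monitoring and precedes the PACU text. Read literally, it would also cover the nausea ratings and the anxiety scale, which are plainly prospective. It may mean mainly intraoperative data. On that reading, however, PACU vomiting has no stated source at all, and the same correction is needed.

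**A reader might infer that the plan inflates nausea relative to vomiting.** The documents do not support this. They offer no evidence that vomiting is under-charted, and vomiting is an observable event that a record might capture over the whole stay. Nausea between momentary ratings can be missed, which pulls the other way.

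**A reader might also try to size the effect from the plan's own percentages.** That does not work. The 33% in G1 is an assumed incidence of nausea and vomiting combined, in children. The 12% in the background is an adult vomiting figure given in a post-discharge context. Neither is a PACU nausea or vomiting rate in children, and their quotient describes nothing in this study.

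**Objective 1 is descriptive.** This also stands. G2 plans incidences, with no test, ratio or power, so no error rate is at risk; what suffers is the interpretation of the estimates. Nor does a gap between two incidences test the background's claim, which concerns correlation.

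**Conclusion.** The point holds as a difference in ascertainment of unknown net direction and size. PACU nausea is prospectively elicited; PACU vomiting has no described study procedure, and record review is the only stated source that could supply it. Missed vomiting would widen the contrast and missed nausea would narrow it, so no inflation factor or ratio can be given. The count problem for severe vomiting is firmer, because it follows from the outcome's definition and the described wording of the phone call.

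The conclusion assumes that the document describes the study procedures in full. A data-collection form that already records emetic episodes would answer it. This is a low-cost improvement and does not undermine the study.

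**What to change.** 1. **PACU form.** At each nausea rating and just before discharge, the evaluator records the number of vomiting or retching episodes since the previous rating. For the first rating the interval runs from PACU arrival. The entries then cover the whole stay, not single moments.
2. **24-hour call.** Ask how many episodes occurred after going home, not only whether there was any vomiting. Added to the PACU counts, this gives the number that the severe-vomiting definition needs.
3. **G2 item (1).** Name these counts as the source for vomiting, with the chart as back-up, and say whether retching alone counts as an episode.

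The cost is one extra line on a form and one extra phone question, both at contacts already planned. Clinical care does not change. The change does not remove the chance of missing nausea between ratings, so the report should still say that nausea was rated at moments while vomiting was counted over intervals.

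### The change question has no stated reference rating or schedule, and the minimal-change and test-retest analyses do not say which two scores each answer belongs to

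*Combined protocol and SAP*

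**What the plan says.** All references are to the combined protocol and SAP.

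- **F2 Procedure, the question.** "After the first set of assessments are done in the PACU, patients will also be asked to rate their nausea" on a five-point scale with the options "1) Much worse than before, (2) A little worse than before, (3) The same as before (4) A little better than before" and, fifth, much better. The comparison point is not defined.
- **F2, the ratings.** Nausea is scored "1) before induction of anesthesia, (2) when awake in the PACU, (3) just before, and (4) 30-60 mins after receiving analgesic or antiemetic therapy", and a fifth time just before discharge. That is one preoperative rating and up to four in the PACU. The text adds "Another set of assessments will be just prior to discharge" without saying whether that set includes the change question.
- **F1, inclusion criterion (4).** Children must be "Free from nausea and / or vomiting in the previous 24 hours".
- **G2, item (3).** The minimal relevant change comes from "subjects who report their nausea as a little worse than before or a little better than before". The two scores to be subtracted are not named.
- **G2, item (5).** Test-retest reliability is "The relationship between the first and subsequent BARF and VAS nausea scores in patients who state their nausea is" the same as before, assessed by Spearman's rank correlation and Cronbach's alpha. Which later score is used, and whether *first* means the first PACU score, is not stated.

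**The concern.** The child's answer does two jobs. It is the anchor that decides which score changes count as minimally relevant (Section D, aim 3), and it is the filter that selects unchanged children for test-retest reliability (aim 5). Both work only if the child compares the same two moments whose scores the analyst later compares.

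The plan fixes neither side. If the question is put straight after the first PACU rating, the only earlier rating is the preoperative one, taken in children who had to be free of nausea and vomiting. If it is put at later ratings, a child would naturally compare with the last rating, while G2 (5) speaks of the first score. Staff could apply either reading. If the question put to the child had no clear reference, nobody can establish afterwards which moment the child had in mind.

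**Working it through.** **1. The plan's own figure.** G1 sizes the minimal-change aim "In order to detect a 1 face difference with 80% power at the 0.05 level of significance", with SD 2.4 and a one-face difference. I enter one face as 1 unit (assumption: the documents do not give the score spacing of the faces) and take the test as two-sided (sidedness is not stated).

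- Two means, normal approximation: 2 × (2.4/1)² × (1.960 + 0.842)² = 90.4, so 91.
- Paired t-test with SD of the difference 2.4 × √2 = 3.39 (zero correlation): 92.4, so 93.

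The stated 93 is reproduced. G1 then takes 93 × 3 = 279 to find 93 children with a changed score at 33% incidence, and recruits 387. The sample size calculation is not in dispute here; I use 279 and 33% to size the answer groups.

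**2. If *before* means the preoperative state.** Assume every baseline score is 0 and that the 33% incidence describes who is nauseated when asked. The documents do not give the incidence at the first PACU rating.

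| Answer | Formula | Of 279 | Of 387 |
|---|---|---|---|
| Worse (a little or much) | 0.33 × N | 92 | 128 |
| The same | 0.67 × N | 187 | 259 |
| Better (a little or much) | 0 | 0 | 0 |

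For G2 (3), the *a little better* arm is empty. The *a little worse* arm is some part of the 92, because *much worse* also draws on them; the documents give no split.

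For G2 (5), the 187 pairs are all 0 and 0. Spearman's rho is undefined for constant scores, and Cronbach's alpha has no variance to work with.

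**3. Relaxing the all-zero assumption.** Suppose 2%, 5% or 10% of children have a non-zero baseline (assumed range).

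| Non-zero baseline | Most who could answer *better* (of 279) | *Same* pairs starting at zero, 0.67 × (1 − b) × 279 | Remaining *same* pairs |
|---|---|---|---|
| 2% | 6 | 183 | 4 |
| 5% | 14 | 178 | 9 |
| 10% | 28 | 168 | 19 |

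The second and fourth columns are separate upper limits; the same child cannot count in both. The last column assumes that non-zero baselines are as common among these children as overall. The coefficients can then be computed, but mainly from a handful of children.

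**4. If the question is asked at later PACU ratings.** Compare the first PACU score with the immediately preceding one.

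- A child rated only when awake and before discharge has two PACU ratings. First and preceding are the same score, so nothing is mismatched.
- A treated child can have four: awake, before therapy, after therapy, before discharge. Of the three later ratings, first and preceding coincide only at the second; at the third and fourth they differ.

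Illustration: a child scores 4 when awake, 8 before therapy, 8 after it, and truthfully answers *the same*. The preceding pair is 8 and 8; first with current is 4 and 8. The second pair enters as retest disagreement although the child reported no change. A mismatch needs three or more PACU ratings and a score that moved between the first and the preceding one. The documents give no frequency for this. Under G2 (3) the same ambiguity applies to the change score.

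**The case against.** The best defence is that the sections, read together, point to an earlier PACU rating as the reference. The F2 phrase can mean at assessments after the first. G2 (5) speaks of first and subsequent scores. G2 (3) plans to use *a little better*, which makes little sense against a nausea-free baseline. On that reading both *better* and *the same* can be populated. This stands as a reasonable reading, but the text does not settle it: G1 counts children with a changed score by applying a PONV incidence, which also fits change from a nausea-free start.

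It can also be said that *first and subsequent* may mean the earlier and later member of any pair, and that all scores are kept, so a poor pairing can be corrected at analysis. That holds if the reference given to the child is known. It does not help if the question itself had none.

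A reader might go further and infer that the preoperative reading empties both the *better* and the *unchanged* groups and makes the reliability coefficients impossible to compute. The documents do not support that. *The same* would be the largest group. Criterion (4) concerns the previous 24 hours and does not fix the score; F2 still measures current nausea before surgery on both scales, and the VAS is a marked line, so small non-zero values are possible. Rho and alpha are undefined only if all scores are exactly 0.

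**Conclusion.** The point holds as a gap in the question and in the score pairing. It does not show that the design must fail.

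- **Preoperative reference:** *better* is nearly empty (0 of 279 with all-zero baselines; at most about 6 to 28 if 2% to 10% are non-zero). *The same* holds about two-thirds of children, nearly all at the floor, with little test-retest information.
- **Later-rating reference:** both groups can be populated, but pairing from the first PACU score can contradict the answer in children with three or more PACU ratings, mainly treated children. How often is unknown.

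The counts rest on the plan's 33% incidence applied at the moment of asking and on the assumed baselines. The absence of a stated reference, schedule and score pair rests on no assumption. It affects two of the five aims and should be settled before data are collected.

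**What to change.** - **F2:** ask the change question at each scheduled PACU rating after the first (before therapy, 30-60 minutes after it, before discharge), worded as *compared with the last time you showed me*.
- **G2 (3) and (5):** compute the change and form the retest pair from the current score and the immediately preceding PACU score, not from the preoperative or the first score.
- **Repeated answers:** a child can then supply up to three pairs, which are correlated. Use one pre-specified pair per child, for example the first eligible one, or use a method that accounts for pairs within a child.

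Naming another single PACU rating as the reference would also remove the ambiguity, provided the wording and the score pair agree. The preceding rating is preferred because it is the comparison a child most naturally makes.

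The cost is one sentence in F2, a short addition to G2, one brief question repeated at ratings already scheduled, and a little more analysis work. No clinical care changes.
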